Adequate records (*Case Report Forms*) will be maintained for the study including subject medical and surgical records, test reports, signed informed forms, and information about subject discontinuation. All original documentation will remain at the investigative sites. Study data that are generated electronically (e.g. corneal topography etc.) will be printed and retained in the study files. A unique identifier will be assigned by the Investigators to each trial subject to protect the subject's identity.

Dropouts/Lost-to-follow-up/withdrawal

Participants may drop out at any time during the study. Based on the scientific literature and considered the 1-year follow-up, a ≤20% dropout may be expected in the study. A total number of 50 participants is therefore allowed to be enrolled in the study.

Statistical Methods

Descriptive statistics will be used to summarize the data: numerical variables will be summarized as mean and standard deviation or median and interquartile range, respectively, according to the distribution of the data; categorical variables will be represented as frequencies and proportions. Student's t-test or Wilcoxon test will be applied to compare continuous variables, while Fisher's exact test or Chi-Squared test will be used to analyze categorical variables. ROC curve analysis will be used to evaluate cut-off values for the theranostic imaging biomarker scores in predicting the propensity of CXL treatment to flatten the K_{max} value at 12-months. The cut-off value for the biomarker scores will be determined by optimizing the Youden index. Moreover, sensitivity, specificity, proportion of correctly classified eyes and positive predictive value (PPV) positive predictive values (PPV) and false negative rate (FNR) and confidence intervals will be calculated. The study set a minimum threshold of 85% for the theranostic software module's accuracy and precision in predicting the propensity of CXL to halt disease progression (intended as more than 0.1 D K_{max} flattening) at 1 year in the study population (per protocol population).

Statistical significance will be set at 0.05. All the analysis will be performed using the statistical software R (latest version available).

Data Analysis

Data will be summarized using descriptive statistics and graphical presentations.

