This clinical investigation is conducted in accordance with the provisions of articles 62 to 80 and Annex XV of the Regulation (EU) 2017/745 as part of the clinical evaluation for conformity assessment purpose of the UV-A theranostic medical device C4V CHROMO4VIS®. The object of the clinical investigation is the validation of the theranostic software module of a CE certified UV-A medical device for the treatment of pathological conditions of the cornea. The device in question conforms to the general safety and performance requirements apart from the aspects covered by the clinical investigation; with regard to those aspects, every precaution has been taken to protect the health and safety of the study participants.

Study protocol overview

Background and State-of-the-Art

Keratoconus is a degenerative corneal disease characterized by tissue weakening and thinning, which lead to corneal bulging (corneal ectasia). The incidence of keratoconus varies between 1:300 and 1:2000 depending upon geographical location (it is more frequent in the south regions of the world). Prevalence of keratoconus is estimated between 0.5% and 3% depending upon geographical location. The etiopathogenesis of keratoconus is multifactorial; familiarity, which is found in 15% - 18% of patients highlights the importance of genetics in the pathological pathway of keratoconus; beyond the genetic heterogeneity of keratoconus, the importance of various environmental factors (UV, atopy), which are able to trigger or accelerate the progression of corneal degeneration, is emphasized in the pathogenesis of the disease.^{1,2} The anatomical alterations of the corneal stroma in keratoconus have been correlated to a biomechanical tissue weakening. A number of experimental and clinical studies has shown decreased stiffness and altered viscoelasticity in keratoconus; the main theory is that tissue bulging is caused by inability of the keratoconic cornea to resist the physiologic intraocular pressure levels.

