Assessing the theranostic software module 2.0

Theranostics is a cutting-edge treatment paradigm. The term “theranostics” refers to the simultaneous integration of therapy and diagnostics and designates a medical solution that provides a precise and personalized therapy for the patient. In this specific case, the medical device C4V CHROMO4VIS 2.0 enables the surgeon to perform the corneal cross-linking procedure by analyzing the images of the corneal tissue to treat.

The C4V CHROMO4VIS 2.0 system provides estimates of the riboflavin concentration in the cornea in real time during treatment, i.e., the riboflavin score, and a predictive index of therapeutic efficacy, i.e. the theranostic score. The purpose of this clinical investigation is to validate the theranostics software v. 2.0 of the medical device in order to determine the threshold of the theranostic imaging biomarker predicting efficacy of the corneal cross-linking procedure, regardless of the CXL treatment protocol.

Theranostic-guided UV-A irradiation plans

For the purpose of this clinical study, the system is pre-programmed with two specific pre-set treatment plans:

- “Theranostic EpiOff CXL” consisting of 15 minutes riboflavin dosing and 9 minutes UV-A irradiation by 10 mW/cm².
- “Theranostic EpiOn CXL” consisting of 20 minutes riboflavin dosing and 9 minutes UV-A irradiation by 10 mW/cm².

Theranostic-guided CXL operation sequence

[figure not shown]
- The device power is turned on by the research medical doctor (the “user” or “operator”). The device then checks for startup errors and if the system is starting up correctly, a device calibration is performed.
- The research medical doctor with Administrator user privilege can authorize the Operator user to access patient database and the operator main panel to set the treatment plan for the cornea to treat and the patient’s information.
- Patient data include the key code of the eligible patient to be treated.
- In the treatment plan screen, the Operator adds the eye to be treated and the corneal parameters (CCT and K_{max}) and confirm to begin treatment.
- The Operator prepares the eye for treatment.
- Once the Operator has focused the system onto the eye, a baseline image of the cornea must be acquired by pressing the foot switch for subsequent theranostic real time image analysis.

- During the application phase, apply one drop of riboflavin ophthalmic solution every 20 second directly onto the cornea of the eye to treat.

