The efficacy and performance of the UV-A medical device in question has been validated in the laboratory on donor eye bank corneal tissues. The laboratory experiments on the UV-A medical device under evaluation were performed in accordance with the principles of the Helsinki Declaration for the use of human tissues in scientific research. The donor corneal tissues were shipped to the manufacturer's laboratory by the Fondazione Banca degli Occhi del Veneto (Venezia Zelarino) after adequate time of cultivation in special media in order to preserve the integrity of the corneal epithelium and the tissue integrity and transparency.

In the first pre-clinical study,⁶ a former group of seven (7) corneal tissues was treated by using the *Dresden protocol*, i.e., with application of riboflavin for 30 minutes and UV-A irradiance of 3 mW/cm² for 30 minutes (total 5.4 J/cm² energy dose). An additional group of ten (10) corneal tissues was probed by atomic force microscopy (AFM) in order to assess the biomechanical properties of the cornea after corneal cross-linking using the *Dresden protocol*. The scope of the study was to evaluate the performance of the present device in improving the corneal biomechanics strength, measured as increased tissue stiffness (i.e., increased Young's modulus). After corneal cross-linking, the average Young's modulus increased significantly from 1.61±0.53 MPa preoperatively to 2.08±0.72 MPa postoperatively (P=0.001). In summary, the results of the laboratory validation have shown that the UV-A medical device in question is effective in performing corneal cross-linking treatment on human eye corneal tissues by increasing the elastic modulus of the corneal tissue. No alteration of the corneal tissues undergoing corneal cross-linking with the UV-A medical device in question was observed.

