- Measurement of **corneal endothelial cell density** (ECD) with specular microscopy will assess will assess changes of the ECD after treatment.
- **Slit lamp biomicroscopy** will assess integrity of the cornea and anterior segment of the eye.

Primary outcome measure

Validation of the Theranostic Imaging Biomarker [Time Frame: 12-months]

- Validation of the combined use of the theranostic imaging biomarkers. True positives, false positives, true negatives and false negatives were evaluated in order to determine the ability of the theranostic imaging biomarkers, including both the *riboflavin score* and *theranostic score*, to predict the propensity of CXL treatment in flattening the K_{max} value (D) by more than 0.1 D at 12 months postoperatively.

Theranostics: confirmation of the theranostic imaging biomarker will be provided at the end of treatment procedure. The theranostic data, which will be recorded during treatment procedure, will be exported to a computer for subsequent analysis with 12-months data.

The accuracy and precision (95% CI) of the combined use of the theranostic imaging biomarkers to predict CXL treatment outcome were determined by calculating the proportion of correctly classified eyes and the positive predictive value (PPV) respectively. The miss rate, which is the probability that a true positive is missed by the theranostic methodology, was determined by calculating the false negative rate (FNR).

The study sets a minimum threshold of 85% for the theranostic software module's accuracy and precision in predicting the propensity of CXL to halt disease progression (intended as more than 0.1 D Kmax flattening) at 1 year in the study population, who participated and completed at least 66% of all the visits (i.e., 4 of 6 total visits) and the last at 12 months (i.e., Per Protocol Population);

Secondary outcome measures

Efficacy [Time Frame: 12-months]

- Change of Maximum Keratometry index assessed by corneal topography at 12-months.

Corneal topography: measurement of maximum simulated keratometry (K_{max} , D) will be done by using Placido disk corneal topography. The investigator will record the K_{max} value at each visit and will fill the corresponding CRF. This test is performed to provide evidence of corneal curvature change after treatment.

Safety [Time Frame: 12-months]

- Change of Endothelial Cell Density assessed by specular microscopy at 12-months.

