Synopsis on disposition of participants

Sample size

By expecting a response rate of 50% of cases that will reach the threshold of -1.05 D of the K_{max} value, a sample size of 42 patients achieves 91% power to detect a difference of 0,25 between the area under the ROC curve (AUC) under the null hypothesis of 0,60 and an AUC under the alternative hypothesis of 0,85 using a two-sided z-test at a significance level of 0,05000. The data are continuous responses. Considering a $\leq 20\%$ drop-out rate (determined from systematic literature review on controlled and open clinical studies on standard and epithelium-on CXL procedures), a number of 50 participants (25 per treatment protocol) is allowed to be enrolled in the study.

Details on the methodology and process used to define the sample size of this clinical trial are described in Appendix 1 – Methodology for sample size calculation.

Statistical methodology

Descriptive statistics will be used to summarize the data: numerical variables will be summarized as mean and standard deviation or median and interquartile range, respectively, according to the distribution of the data; categorical variables will be represented as frequencies and proportions. Student's t-test or Wilcoxon test will be applied to compare continuous variables, while Fisher's exact test or Chi-Squared test will be used to analyze categorical variables. Bonferroni correction is applied to analysis of exploratory outcome measures of stratification groups. For all reported AEs, the data can be presented with events listed in order of decreasing frequency.

The optimal cut-off values in predicting the propensity of CXL treatment to flatten the Kmax value at 12-months was determined based upon the results of preclinical studies (data not disclosed to investigators to avoiding methodological study bias) and can be optimized with the Youden index. The accuracy and precision (95% CI) of the combined use of the theranostic imaging biomarkers to predict CXL treatment outcome will be determined by calculating the proportion of correctly classified eyes and the positive predictive value (PPV) respectively. The miss rate, which is the probability that a true positive is missed by the theranostic methodology, will be determined by calculating the false negative rate (FNR).

Statistical significance will be set at 0.05. All the analysis will be performed using the statistical software R (latest version available).

Population to be analysed

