- Average Treatment Efficacy Index (day 0).
- Number of subjects completing visits after treatment.
- number of premature terminations/drop-outs.
- Average UDVA at each visit.
- Average CDVA at each visit.
- Average manifest refraction at each visit.
- Average ECD at each visit.
- Slit lamp biomicroscopy data at each visit.
- Interim analysis of primary outcome measure at 6-months.
- Adverse events (number and type).
- Missing data.
- Other information (if any).

A final report (Annex 7) shall be elaborated in written (English) according the ICH E3 guidance on structure and content of clinical study reports and sent to the Sponsor for approval. The Final Report will compile all the data collected from all the participants during the entire duration of the study (from screening to the end of follow-up, including AE (if any), discussion of statistical analysis as well as interpretation of the results. This report will be sent to the Sponsor within 2 weeks from the final

monitoring visit performed by the Sponsor to confirm the correctness and completeness of the data collected and database lock. In the Final Report, a clear conclusion on the following points must be provided:

- Assessment of primary outcome measure at 12 months (day 360), such as:
 - Validation of the combined use of the theranostic imaging biomarkers. True positives, false positives, true negatives and false negatives were evaluated in order to determine the ability of the theranostic imaging biomarkers, including both the *riboflavin score* and *theranostic score*, to predict the propensity of CXL treatment in flattening the K_{max} value (D) by more than 0.1 D at 12 months postoperatively.
- Assessment of all secondary outcome measures, such as:
 - Change of Maximum Keratometry assessed by corneal topography at 12-months.
 - Change of Endothelial Cell Density assessed by specular microscopy at 12-months.
- Assessment of the additional exploratory outcome measures, such as:
 - Change of Corrected Distance Visual Acuity (CDVA) assessed by ETDRS at 12-months.
 - Change of Uncorrected Distance Visual Acuity (UDVA) assessed by ETDRS at 12-months.
 - Change of Manifest Refraction assessed by ETDRS at 12-months.
 - Change of secondary outcome measures at 12-months in either stratification group.

Study Reporting Requirements

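### The plan does not settle whether the biomarker cut-off is pre-set or tuned on the study's own eyes; if tuned, the accuracy and PPV judged against 85% are biased upward

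*Combined protocol and SAP*

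**What the plan says.** Three parts of the combined protocol and SAP describe where the cut-off comes from.

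- **Synopsis, Statistical Methods:** "ROC curve analysis will be used to evaluate cut-off values for the theranostic imaging biomarker scores in predicting the propensity of CXL treatment" to flatten Kmax at 12 months, followed by "The cut-off value for the biomarker scores will be determined by optimizing the Youden index". Both are in the future tense and tied to this study's outcome.
- **Statistical methodology:** the cut-off has already been determined, from "preclinical studies (data not disclosed to investigators to avoiding methodological study bias) and can be optimized with the Youden index". The data set, trigger and date for that optimisation are not given.
- **Assessing the theranostic software module 2.0:** the investigation is meant to "determine the threshold of the theranostic imaging biomarker predicting efficacy of the corneal cross-linking procedure, regardless of the CXL treatment protocol". Youden is not mentioned there.

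The Primary outcome measure section calls the exercise validation. "The accuracy and precision (95% CI) of the combined use of the theranostic imaging biomarkers to predict CXL treatment outcome" are defined as the proportion of eyes correctly classified and the PPV. Both are held to a minimum of 85% in the per-protocol population, and the false negative rate is also reported. A positive outcome is Kmax flattening of more than 0.1 D at 12 months. The primary outcome uses the riboflavin score and the theranostic score together, but the protocol text gives no rule for combining them. The Reports section also lists "Interim analysis of primary outcome measure at 6-months".

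**The concern.** A cut-off that maximises the Youden index in a small sample partly fits the chance pattern of that sample. Accuracy and PPV computed on the same eyes are then too high and the false negative rate too low. That is cut-off development, not validation. No hold-out set, cross-validation or optimism correction is described, and no date is set for freezing the cut-off.

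The study is run "as part of the clinical evaluation for conformity assessment purpose of the UV-A theranostic medical device", so the 85% criterion carries regulatory weight. With the sections in conflict, either a tuned or a pre-set cut-off could be reported as the primary result, and a reader could not tell which it was. Withholding the preclinical data from investigators protects little if the cut-off can later be re-chosen against outcomes.

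**Working it through.** **1. The plan's own figure.** The sample size section gives 91% power with 42 patients (AUC 0.60 against 0.85, two-sided 0.05, 50% responders, so 21 and 21). With the Hanley-McNeil variance, SE is 0.0880 under the null and 0.0608 under the alternative. Power = Φ((0.25 − 1.96 × 0.0880)/0.0608) = Φ(1.28) = 89.9%, close to 91%. The plan does not name its variance formula. AUC needs no cut-off, so this calculation is not touched by the concern.

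**2. Share of eyes flattening by more than 0.1 D.** The plan does not give it. Normal approximations to the 1-year Kmax changes in Appendix 1:

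- All cases, −1.05 ± 0.80 D: Φ((−0.1 + 1.05)/0.80) = 88%
- Standard (Epi-OFF), −1.41 ± 1.71 D: Φ((−0.1 + 1.41)/1.71) = 78%
- Transepithelial (Epi-ON), −0.32 ± 1.55 D: Φ((−0.1 + 0.32)/1.55) = 56%
- 1:1 mix of the last two: 67%

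In 42 eyes, 67% is 28 responders and 88% is 37. The plan's 50% refers to reaching −1.05 D, so 21 responders is a sensitivity case only.

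**3. Simulation.** Assumed: one equal-variance binormal score, with class means √2 × Φ⁻¹(0.85) = 1.466 SD apart. In each of 6,000 replicates the cut-off with the largest sensitivity + specificity − 1 was chosen on the 42 eyes (ties at random). Apparent figures come from those eyes; true figures come from the normal model at the chosen cut-off. The Monte Carlo standard error of the accuracy bias is about 0.07 points.

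| Responders of 42 | Accuracy, apparent / true | PPV, apparent / true | FNR, apparent / true |
|---|---|---|---|
| 28 (67%) | 81.2 / 75.5 | 91.0 / 86.3 | 19.6 / 23.9 |
| 37 (88%) | 81.4 / 77.1 | 98.3 / 95.4 | 19.6 / 22.0 |
| 21 (50%, sensitivity) | 81.3 / 75.3 | 82.7 / 76.7 | 18.6 / 24.7 |

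Over AUC 0.75 to 0.90 at the 67% and 88% shares, accuracy is overstated by 3.8 to 6.7 points and PPV by 2.5 to 6.0; FNR is understated by 2.1 to 5.0. With 40 eyes (27 and 35 responders) the accuracy bias is 6.0 and 4.5 points.

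**4. Can it change the verdict?** At AUC 0.85 and 67% responders, both apparent figures reach 85% in about 30% of tuned samples. True accuracy cannot reach 85% at any cut-off there; its maximum is about 79%. At AUC 0.90 and 67% responders, mean apparent accuracy is about 85.7% and true accuracy about 80.5%.

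**5. A cut-off locked in advance.** Its observed figures carry no selection bias, but its true accuracy depends on where it lies. At AUC 0.85, with the cut-off 0.5 SD below, at, and 0.5 SD above the mid-point between class means, true accuracy is 79.1, 76.8 and 69.2% (67% responders) or 85.6, 76.8 and 62.8% (88%). The preclinical value is undisclosed, so no pass-rate comparison of tuned against locked is claimed.

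**6. Do corrections work?** In 2,000 separate replicates (21/28/37 responders), true accuracy was 75.3/75.4/77.1%. Ten repeats of stratified five-fold cross-validation, with the cut-off search repeated in each training set, gave 74.9/75.2/77.0%. Plain bootstrap optimism subtraction (80 resamples) gave 77.2/77.5/78.8%, removing only 67/63/57% of the bias.

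**The case against.** The strongest reply is that the Statistical methodology section governs: the cut-off was set beforehand, withheld from investigators to avoid bias, and Youden is only optional. The Primary outcome measure section also has the biomarker confirmed at the end of the procedure, which fits a call made before any Kmax outcome exists. On that reading the bias does not arise. This is a fair reading, but the synopsis says the opposite and the software module section leans the same way. What is certain is the conflict; the bias is conditional on tuning.

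Other points stand in part:

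- A combination rule or software lock may be in the Investigator's Brochure or the User Manual, which were not available. The remark about the missing rule applies to the protocol text only.
- Nothing links the 6-month interim to cut-off choice. It matters only because the plan does not say the cut-off is frozen by then.
- The 88% share rests on an SD of 0.80 D, while the trial-level SDs in Appendix 1 are 1.55 and 1.71 D. It is best read as a high case.
- The per-protocol set could hold 40 to 50 eyes before major deviations are removed. This changes the bias little.
- In both main scenarios at AUC 0.85, mean accuracy is below 85% and mean PPV above it, tuned or true. The effect on the verdict shows in individual samples and at AUC 0.90, as in steps 3 and 4 of the working.
- Cross-validation removes the average bias but is noisy with five non-responders. Its root mean square error for true accuracy was 8.3 points, against 6.7 uncorrected, at 88% responders; at 67% it was better, 6.6 against 7.9.

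**Conclusion.** The concern holds. Two current sections give incompatible rules for the cut-off behind the primary result. Followed as written, the synopsis yields a biased primary estimate: accuracy about 4 to 6 points too high at AUC 0.85 with about 42 eyes, PPV about 3 to 5 points too high, and FNR about 2 to 4 points too low. These sizes rest on a single equal-variance binormal score and on responder shares approximated from Appendix 1. The effect of tuning two scores jointly is not sized, because no combination rule is stated. If the preclinical cut-off is used unchanged, this bias is absent.

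**What to change.** Reconcile the synopsis, the software module section and the Statistical methodology section so that one cut-off rule and one stated rule for combining the two scores feed the primary accuracy, PPV and FNR.

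- **Preferred:** use the existing preclinical cut-offs, locked and dated before any post-treatment Kmax is analysed together with the scores, including at the 6-month interim. Report any Youden-optimised cut-off as exploratory and optimism-corrected. The value can stay undisclosed to investigators if the lock record exists.
- **Alternative, if in-study Youden selection stays primary:** report accuracy, PPV and FNR from repeated stratified cross-validation that repeats the cut-off search, and any fitting of the combination, in every training fold. Judge 85% on those figures, name the method for the 95% confidence interval the plan requires, and call the result cut-off development. Plain bootstrap subtraction alone is not enough.

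The cost is revised wording plus a dated lock record or a short R script; no extra patients are needed. Reported accuracy and PPV may come out lower than the in-sample figures. The preferred route has its own risk: the preclinical efficacy work described "has been validated in the laboratory on donor eye bank corneal tissues", without a 12-month Kmax outcome, so a locked cut-off could be poorly placed and do worse than a tuned one. That is why the cross-validated route is also acceptable.

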Technical Features

FEATURE	TREATMENT		LIGHT SOURCE
UV irradiance	UV irradiance	[REDACTED]	[REDACTED]
	UV exposure time	[REDACTED]	[REDACTED]
	UV emission	[REDACTED]	[REDACTED]
	Measured points	[REDACTED]	[REDACTED]
	Corneal coverage	[REDACTED]	[REDACTED]
	Focusing system	[REDACTED]	[REDACTED]
Power monitoring	Double check system	[REDACTED]	[REDACTED]

Optical Radiations

FEATURE	LIGHT SOURCE	WAVELENGTH	POWER DENSITY ON EYE
Central fixation LED	[REDACTED]	[REDACTED]	[REDACTED]
Illumination of Placido disk for alignment and focusing	[REDACTED]	[REDACTED]	[REDACTED]
UV-A light source	[REDACTED]	[REDACTED]	[REDACTED]

Environmental Conditions

	IN USE	STORAGE	TRANSPORT
Temperature	[REDACTED]	[REDACTED]	[REDACTED]
Relative humidity	[REDACTED]	[REDACTED]	[REDACTED]
Atmospheric pressure	[REDACTED]	[REDACTED]	[REDACTED]

Electrical Data

Power supply		[REDACTED]
Power consumption		[REDACTED]
Fuse	Type	[REDACTED]
	Value	[REDACTED]

On-Board PC Specifications

Operating system	[REDACTED]
Processor	[REDACTED]
RAM	[REDACTED]
Hard disk	[REDACTED]
External connections	[REDACTED]

Touch Screen

Dimension	[REDACTED]
Ratio	[REDACTED]
Resolution	[REDACTED]
Rotation	[REDACTED]
External connections	[REDACTED]

System Mechanical Features

Width (max)	[REDACTED]
Height (max)	[REDACTED]
Length (max)	[REDACTED]
Weight	[REDACTED]
Cart wheels	[REDACTED]
Degrees of freedom of the balanced arm	[REDACTED]

[figure not shown]
Main UV-A medical device operation

- Before any intervention, the C4V CHROMO4VIS must be placed adjacent to the treatment table or chair, away from bright lights, such as positioning in front of windows and the casters must be locked to secure the device's position.
- The device power is turned on by the medical doctor (the “user” or “operator”). The device then checks for startup errors and if the system is starting up correctly, a device calibration is performed.
- The system includes three types of users, such as the Administrator, the Operator (i.e., the surgeon) and the Service. Only the Administrator has database-level privilege and can add/delete surgeons. Therefore, to access patient database, the Operator must be authorized by the Administrator, who has database-level privilege. Once authorized by the Administrator, the Operator can access to the operator main panel and set the treatment parameters for the cornea to treat and the patient's information.
- To begin preparing for treatment, the user enters and/or select the treatment settings:

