- During the application phase, the system tracks the application time of riboflavin and notifies the user that the induction is complete. The system provides the Operator with an index estimating the concentration of riboflavin into the cornea.
 - EpiOFF protocol: before measuring the riboflavin concentration into the cornea, dry the corneal surface with a tnt stick.
 - EpiON protocol: before measuring the riboflavin concentration into the cornea, rinse the corneal surface with balanced salt solution.
- The UV-A treatment is then performed. The device tracks the UV-A treatment time, turns off the UV-A and notifies the user when the treatment has been completed. The system provides the Operator with an index estimating the treatment efficacy, i.e., the theranostic imaging biomarker.
 - The operator may choose to rinse the corneal surface with balanced salt solution at 5 minutes interval during UV-A irradiation.
- Once the treatment has been completed, the Operator save the treatment report in a USB stick for printing and adding it to the medical patient record.
- The Operator may choose to treat another eligible patient or the device may be powered off.

Pre-clinical studies on safety of the UV-A medical device

[figure not shown]
The C4V CHROMO4VIS system has been designed and built in full compliance with EU Directive 93/42/EEC. The medical device has undergone safety testing according to the following standards:

- EMC EN 60601-1-2
- EN 60601-1
- ISO 15004-2:2007
- EN 64271:2010

Results of the emission and immunity testing

[REDACTED]	[REDACTED]	[REDACTED]	[REDACTED]	[REDACTED]	[REDACTED]
[REDACTED]	[REDACTED]	[REDACTED]	[REDACTED]	[REDACTED]	[REDACTED]
[REDACTED]	[REDACTED]	[REDACTED]	[REDACTED]	[REDACTED]	[REDACTED]
[REDACTED]	[REDACTED]	[REDACTED]	[REDACTED]	[REDACTED]	[REDACTED]
[REDACTED]	[REDACTED]	[REDACTED]	[REDACTED]	[REDACTED]	[REDACTED]

Pre-clinical studies on efficacy of the theranostic UV-A medical device

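### The available text neither masks the day-360 Kmax examiner to the theranostic scores nor fixes which scan counts, so knowing the score can raise the accuracy it is judged on, by about 1 to 2 of 42 eyes under an assumed 0.25 D shift

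*Combined protocol and SAP*

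**What the plan says.** Both scores reach the treating surgeon. Under Theranostic-guided CXL operation sequence, during riboflavin application, "The system provides the Operator with an index estimating the concentration of riboflavin into the cornea"; after irradiation, "The system provides the Operator with an index estimating the treatment efficacy", which the plan equates with the theranostic imaging biomarker. Main UV-A medical device operation identifies the operator as the surgeon. At the end of treatment "the Operator save the treatment report in a USB stick for printing and adding it to the medical patient record".

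The scores also return to the sites in summary. Under Reports, each site writes an interim report on patients who have completed day 180. Its contents include the average riboflavin concentrations and average Treatment Efficacy Index from day 0, and an interim analysis of the primary outcome at 6 months.

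On the outcome side, Secondary outcome measures has the investigator record the Kmax "value at each visit and will fill the corresponding CRF", using Placido topography. Primary outcome measure classes eyes at more than 0.1 D flattening at 12 months and sets an 85% minimum for accuracy and for precision (PPV).

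Three provisions bear on the risk. Statistical methodology says the preclinical basis of the cut-off is not disclosed to investigators, to avoid bias, and also that the cut-off can be optimised with the Youden index. The Synopsis has electronic output such as topography printed and kept in the study files. Primary outcome measure has theranostic data exported for later analysis with the 12-month data. No available passage masks the Kmax examiner, limits repeat scans or names the map that counts.

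**The concern.** The study exists to validate a predictor, so the outcome should be measured without knowledge of it. Here the score is known at the site from day 0, and the outcome is a dichotomy at a very small change. Kmax comes from an instrument, but repeating an acquisition and accepting a map are human choices. If an unexpected reading is more likely to be repeated when it disagrees with the score, the two will agree more often than they should.

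Hiding the cut-off does not close this route. A high or low index is visible without a threshold, an AUC uses no threshold, and the cut-off may be re-optimised on study data. At stake is the primary verdict against 85%. With 42 eyes one eye is 1/42 = 2.4 points, and the bar falls between 35/42 (83.3%) and 36/42 (85.7%).

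**Working it through.** **The plan's own figure.** The Sample size section gives 91% power for AUC 0.85 against 0.60 with 42 patients, half of them responders. With 21 and 21 eyes, the Hanley-McNeil standard errors are SE0 = 0.0880 and SE1 = 0.0608. Power = Φ((0.25 − 1.96 × 0.0880)/0.0608) = Φ(1.28) = 89.9%; the large-sample variance form gives 90.9%. The figure reproduces, and masking does not alter it.

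**Inputs for the size of the risk (Appendix 1).** One-year Kmax change, taken as normal: pooled −1.05 ± 0.80 D, or a 1:1 mix of standard (−1.41 ± 1.71 D) and transepithelial (−0.32 ± 1.55 D). The cut is −0.1 D. The shift d is an assumption, because the documents give no Kmax repeatability.

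**Eyes near the cut.** Let p be the share below −0.1 D, L the share within d below the cut, and U the share within d above it. For d = 0.25 D:

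| Inputs | p | L | U | L + U | Eyes per 42 |
|---|---|---|---|---|---|
| Pooled | 0.8825 | 0.0733 | 0.0507 | 0.124 | 5.2 |
| 1:1 mix | 0.6673 | 0.0550 | 0.0519 | 0.107 | 4.5 |

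**Gain in accuracy.** Suppose every eye is read d further in the direction its score predicts. Only eyes that disagreed with the score and lie within d of the cut can change, and all of them move into agreement. If score errors within d of the cut occur at the overall rates,

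gain = FNR × L + FPR × U.

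The score cut is set so that the share of score-positive eyes equals p.

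*Score with no predictive value* (FNR = 1 − p, FPR = p):
- Pooled: 0.1175 × 0.0733 + 0.8825 × 0.0507 = 0.053. Accuracy goes from 79.3% to 84.6%.
- Mix: 0.3327 × 0.0550 + 0.6673 × 0.0519 = 0.053. Accuracy goes from 55.6% to 60.9%.

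*Score with AUC 0.85* (equal-variance binormal, depending on outcome class only):
- Pooled, baseline accuracy 88.0%, FNR 6.8%, FPR 51.1%: 0.068 × 0.0733 + 0.511 × 0.0507 = 0.031.
- Mix, baseline accuracy 78.7%, FNR 16.0%, FPR 32.0%: 0.160 × 0.0550 + 0.320 × 0.0519 = 0.025.

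The range is therefore about 2.5 to 5 points, or 42 × 0.025 = 1.1 to 42 × 0.053 = 2.2 eyes. If a score of similar AUC instead tracks the size of the Kmax change, its errors cluster near the cut and the gain is about 5 points.

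**Smaller shift.** For d = 0.1 D, L and U are 0.0265 and 0.0228 (pooled) or 0.0217 and 0.0212 (mix). Gains are 2.3 and 2.1 points for the uninformative score, and 1.4 and 1.0 points at AUC 0.85.

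**Effect without a known cut-off.** By simulation, an uninformative score with readings shifted by 0.25 D per standard deviation of the score has its AUC rise from 0.50 to 0.66 (pooled) or 0.57 (mix), and its accuracy rise by about 2 or 4 points. The hidden threshold does not prevent this.

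**The case against.** The strongest reply is that Kmax is a machine reading, the preclinical cut-off is hidden, printouts are retained and monitors check the CRFs. Much of this stands. Transcription can be audited, and the documents show an opportunity for bias, not its occurrence. What these controls do not settle is which of several maps becomes the recorded value. Hiding the threshold is an acknowledgement of the same risk, but it leaves the score itself visible.

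Three stronger readings are tempting, and the documents do not support them.
- A reader might count every eye within 0.25 D of the cut as a possible gain: 4.5 to 5.2 eyes, or 11 to 12 points. Eyes that already agree with the score cannot add to accuracy, so the gain is at most about half that.
- A reader might infer that the day-360 examiner is the surgeon, or reads Kmax with the treatment report in view. The text says neither. That the filed report shows the efficacy score is itself an inference from the operation sequence and from the sites' having to report its average. The CRF and user-manual annexes are not available, and some passages were removed, so a separation of roles stated there cannot be excluded.
- A reader might infer that a worthless score would pass the 85% accuracy bar. On pooled inputs it reaches 84.6% at 0.25 D and passes only with a larger assumed shift (88.5% at 0.5 D). On the protocol mix it stays at 66.0% even then.

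**Conclusion.** The point holds as an avoidable opening for review bias in the primary analysis; it does not show that the results will be biased. Score knowledge at the sites is planned, the outcome is recorded there, and the available text has no masking or acquisition rule. The partial safeguard covers the threshold only.

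The size is modest: about 1 to 2 of 42 eyes for a 0.25 D shift and about 1 eye or less for 0.1 D. It rests on normal distributions with the Appendix 1 means and SDs, a score cut matched to the responder share, and every eye shifting by the full assumed amount. The last assumption is pessimistic. One or two eyes can still decide a result close to 85%, and the remedy is cheap, so the plan should be changed.

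**What to change.** 1. Fix in advance which baseline and day-360 acquisition counts, for example the first map that passes the topographer's quality check, and take the primary Kmax from the exported topographer file.
2. Keep the original treatment report at the site, as the Synopsis requires for original documents, but sealed or filed apart from the follow-up chart and CRF until day-360 Kmax is locked. It stays available if needed for patient care.
3. Until then, remove from the site interim reports the average riboflavin concentrations, the average Treatment Efficacy Index and the 6-month analysis of scores against outcome.
4. Merge scores with Kmax only after Kmax is locked.

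The cost is some filing and data-flow work, with no change to treatment, visits or sample size and no extra reader. Masking remains partial, because the operator still sees the index on day 0.
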